4.1 Inclusion Criteria

To be eligible to participate in this study, an individual must meet all the following criteria:

1. A Registered Nurse at NYULH
2. Willing to provide an email address or cell phone number of choice
3. Willing to attend one workshop in person at The MET and one virtually via WebEx
4. Willing and able to provide consent
5. Age 18 years of age or older

4.2 Exclusion Criteria

An individual who meets any of the following criteria will be excluded from participation in this study:

1. Not a Registered Nurse at NYULH
2. Not willing to provide an email address or cell phone number of choice
3. Not willing to attend one workshop in person at The MET and one virtually via WebEx

4.3 Vulnerable Subjects

The subjects in this study will be employees at NYULH. The study will only include the subject's email or phone number (for SMS texting only) of choice and no other identifiable information will be collected. All results will be analyzed and reported in aggregate and once the data is collected emails will be destroyed by the PI. Study team members are not direct supervisors of any potential participants. One of the art immersion program workshops will be held at the MET, the other session will be held virtually over WebEx. Research will be conducted outside of work hours where possible and appropriate to minimize the risk of breach of confidentiality. No data will be collected at The MET or any virtual session. All research data will be collected via REDCap survey that will be sent as a link in an email or text message depending on the participants preference. The goal of this nursing study is to study the impact of an art immersion program on nurses and therefore the subjects must be nurses.

Participation is voluntary. Decision whether or not to take part in this study will have no impact on the participants' employment status, salary, or performance evaluation at NYU Langone Health.

4.4 Strategies for Recruitment and Retention

Passive recruitment strategies will be used to minimize any coercion/undue influence. Recruitment will be conducted so to ensure employees initiate contact with the study's investigators and to self-identify as an interested participant in a way that maintains their confidentiality, rather than methods by which an investigator approaches or solicits specific employees.

All subjects will be recruited through a recruitment email to specific nursing lists that [name] is the administrator over (# PhD-EdD Nursing Council <#[contact]>, #EdD/PhD council # DNP Council <#[contact]> and campus specific Research Councils# Research Council <#[contact]>) and study flyers will be available in person at staff meetings and other professional nursing forums that include Annual Nursing Science Day, Nurse Week Events Competency Training sessions). Recruitment email will be sent up to 3 times over a month to maximize participation. No direct supervisors of any potential subject will be involved in recruitment to minimize coercion. The PI [name] will be responsible for sending recruitment emails.

An additional recruitment email will be sent via #_All_Nurses to all NYU Langone Health nurses in month 7 of the study, due to low enrollment in previous recruitment attempts. The email will be sent on behalf of the PI, [name], who has no supervisory role over any nurses at NYU Langone Health.

CONFIDENTIAL

This material is the property of the NYU Langone Health. Do not disclose or use except as authorized in writing by the study sponsor

To increase enrollment, [name] will add the sessions and a link to the REDCap as posted classes in the Health Sciences Library calendar of classes and events. The sessions will also be posted on nursing websites and in the CIAC newsletter.

Approval from Department of Human Resources will be obtained recruitment of employees.

4.5 Duration of Study Participation

The duration of the study for participants will not exceed 6 months.

4.6 Total Number of Participants and Sites

Up to 60 participants will be enrolled from different campuses of NYU Langone Health.

4.7 Participant Withdrawal or Termination

4.7.1 Reasons for Withdrawal or Termination

Participants are free to withdraw from participation in the study at any time.

4.7.2 Handling of Participant Withdrawals or Termination

Participants who wish to withdraw may do so at any time with no consequence to their employment. There is no need to notify the PI, they may cease participation in the program or decline to complete surveys at their own discretion.

4.7.3 Premature Termination or Suspension of Study

This study may be temporarily suspended or prematurely terminated if there is sufficient reasonable cause. Written notification, documenting the reason for study suspension or termination, will be provided by the suspending or terminating party to the IRB. If the study is prematurely terminated or suspended, the PI will promptly inform the IRB and will provide the reason(s) for the termination or suspension.

Circumstances that may warrant termination or suspension include, but are not limited to:

- Determination of unexpected, significant, or unacceptable risk to participants
- Insufficient compliance to protocol requirements
- Data that are not sufficiently complete and/or evaluable

Study may resume once concerns about protocol compliance and data quality are addressed and satisfy the IRB.

5 Study Schedule

Activity	Enrollment and Baseline Month 0	Month 1.5	Month 3	Month 6
Informed Consent	X			
Demographic Survey	X			
Cultural Assessment Survey	X			X
Interpersonal Reactivity Index	X			X
Art Workshop 1		X		

CONFIDENTIAL

This material is the property of the NYU Langone Health. Do not disclose or use except as authorized in writing by the study sponsor

Optional Self-directed Activity			X	
Art Workshop 2				X
Post-Intervention Qualitative Survey				X
Additional Art workshops, due to low enrollment (1 in person, 1 online)				x

5.1 Screening

There is no official screening by study staff.

5.2 Enrollment/Baseline

Enrollment/Baseline Collection (Day 0)

- Obtain signed electronic consent from participant via REDCap.
- Participant will complete demographic information, baseline CAS and IRI surveys

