5.3 Intermediate Visits

Art Immersion Class 1 (1-2 months from baseline)

- In-person workshop at the MET

Optional Self-Directed Activity (1.5 months from baseline)

- Independent self-directed reflective exercise with art materials and prompts provided by the MET.

Art Immersion Class 2 (3-4 months from baseline)

- Virtual workshop with MET staff via WebEx

Art Immersion Class 3

- Additional in-person workshop at the MET, added due to low enrollment in previous sessions

Art immersion Class 4

- Additional virtual workshop with MET staff via WebEx, for same reason as above

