9.2 Sample Size Determination

The target sample size is 60 NYULH nurses. Sample size calculations were performed in G*Power with the following parameters

- Test statistic: Dependent samples t-test
- Effect size estimation=0.4
- Type I error probability=0.90
- Type II error probability=0.05

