9.3 Statistical Methods

Demographics will be reported with descriptive statistics including means and frequency counts.

The main objective, to determine whether visual arts training by museum educators increases nurses' skill in cultural competency and personal reflection, will be assessed with a dependent samples t-test. We will compare CAS and IRI at baseline and post-program to find if there is a significant difference in mean scores.

The secondary objective, to understand nurse beliefs about the pedagogical value of visual arts education to nursing practice, will be explored via qualitative survey (attached as separate document) and thematically analyzed.

10 Source Documents and Access to Source Data/Documents

REDCap will be the primary data collection instrument for the study.

Access to study records will be limited to IRB-approved members of the study team. The PI will permit study-related monitoring, audits, and inspections by the IRB, the sponsor, government regulatory bodies, and University compliance and quality assurance groups of all study related documents (e.g. source documents, regulatory documents, data collection instruments, study data etc.). The PI will ensure the capability for inspections of applicable study-related facilities.

Participation as an investigator in this study implies acceptance of potential inspection by government regulatory authorities and applicable University compliance and quality assurance offices.

11 Ethics/Protection of Human Subjects

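### A second CAS/IRI pre-score in the unused weeks before a nurse's first class is a cheap, conditional gain in precision; the single pre-score is not an error

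*Combined protocol and SAP*

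**What the plan says.** Before the program, CAS and IRI are collected once, at Day 0: "Participant will complete demographic information, baseline CAS and IRI surveys" (5.2; the section 5 schedule table shows the same). Section 5.3 then lists "Art Immersion Class 1 (1-2 months from baseline", and the schedule table puts that workshop at Month 1.5. Neither place has a survey in between.

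The primary analysis in 9.3 is a dependent samples t-test on that one score: "We will compare CAS and IRI at baseline and post-program to find if there is a significant difference in mean scores".

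Enrolment is capped ("Up to 60 participants will be enrolled from different campuses of NYU Langone Health", 4.6). Sections 4.4 and 5.3 report low enrolment, answered with a further mailing in month 7 and an extra pair of classes. Surveys travel as REDCap links by email or text (4.3), and nurses sign up for class dates straight after the baseline surveys (6.1). Section 4.7.2 lets them leave surveys unanswered without telling anyone.

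The sample size inputs in 9.2 are "Test statistic: Dependent samples t-test", "Effect size estimation=0.4", "Type I error probability=0.90" and "Type II error probability=0.05", with a target of 60.

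**The concern.** In a paired comparison, all the short-term noise in the pre-score goes into each nurse's change. Here that score is taken once, well ahead of exposure, and the waiting period goes unused although the means of sending another survey already exist. With a cap of 60 and slow recruitment, adding nurses is hard, so more precision per nurse is the practical lever.

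There is a second cost. The study has one cohort and no control group. With a single pre-score, drift or a retest effect before the program cannot be seen at all. A score close to the first class would be the design's only pre-exposure check on either.

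**Working it through.** **Inputs from the protocol.** Paired t-test, effect size 0.4 and target 60 (9.2). I read 0.4 as mean change divided by the SD of change (dz).

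**Inputs assumed.** Alpha 0.05, because the printed type I error of 0.90 cannot be a test level. Two-sided, because 9.3 looks for a difference, although the hypothesis in 9.1 is directional. All 60 nurses give complete pairs. Equal SDs at each time. The protocol gives no SD, no correlation and no dropout rate. The calculation applies to one score at a time.

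**Step 1: the plan's own figure.** Power comes from the noncentral t distribution with n-1 degrees of freedom and noncentrality dz x sqrt(n). For dz = 0.4 and alpha 0.05, 90% power needs 68 pairs two-sided or 55 one-sided; 95% needs 84 or 70. The error rates taken literally need 9 pairs or fewer. None of these gives 60. Two-sided 85% power needs 59, but 9.2 does not state 85%. At n = 60 the noncentrality is 0.4 x sqrt(60) = 3.10, and power is 86.2% two-sided or 92.2% one-sided. The 86% is therefore a recomputation and appears nowhere in the protocol.

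**Step 2: effect of averaging two pre-scores.** Let r be the correlation of either pre-score with the post-score, and r12 the correlation between the two pre-scores. With unit SDs:

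- one pre-score: Var(change) = 2(1 - r)
- mean of two: Var(change) = 1 + (1 + r12)/2 - 2r
- ratio = 1 - 0.25f, where f = (1 - r12)/(1 - r)

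Here f is the share of change-score variance that is short-term within-person noise. Example: r = 0.6 and r12 = 0.8 give f = 0.2/0.4 = 0.5 and a ratio of 0.875. The new effect size is 0.4/sqrt(ratio).

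**Step 3: results, two-sided alpha 0.05, everyone returning both pre-surveys.**

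| f | ratio | dz | power, 60 pairs | power, 40 pairs | pairs matching 86.2% |
|---|---|---|---|---|---|
| 0 | 1.0000 | 0.400 | 86.2% | 69.4% | 60 |
| 0.25 | 0.9375 | 0.413 | 88.2% | 72.2% | 57 |
| 0.50 | 0.8750 | 0.428 | 90.3% | 75.1% | 53 |
| 0.75 | 0.8125 | 0.444 | 92.2% | 78.1% | 50 |
| 1 | 0.7500 | 0.462 | 94.0% | 81.3% | 46 |

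If correlation instead decays with time, with or without added measurement noise (enrolment-to-post r of 0.5 to 0.8), power at 60 pairs is 91-94%. One-sided, the move is from 92.2% to 97.1% at f = 1.

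**Step 4: incomplete return of the extra survey.** If half the nurses return it and the rest keep the enrolment score, the average variance ratio is roughly 1 - 0.125f. That gives 0.9375 (88.2%) at f = 0.5 and 0.875 (90.3%) at f = 1.

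**Step 5: break-even on burden.** From the last column of the table, the gain is gone once more than 60 - 57 = 3 pairs (f = 0.25), 60 - 53 = 7 (f = 0.5) or 60 - 46 = 14 (f = 1) are lost because of the extra survey.

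**The case against.** The strongest reply is that nothing here is wrong. One baseline and a paired t-test is a standard design, and the plan describes it consistently. That stands, and the point is offered only as an improvement.

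A reader might infer that power would rise from 86% to 90-94% with the same nurses. The documents do not support that as an unconditional statement. The starting figure needs assumptions that 9.2 does not supply, and a one-sided test would already pass 90%. Reaching 90% needs about half or more of the change variance to be short-term noise, together with full return of the extra survey.

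Nor can it be every nurse. Those past their first class have no second pre-score to give. Classes 3 and 4 have no stated interval from baseline in 5.3, and the schedule table lists the added workshops under Month 6, so a gap is not established for late recruits.

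The second score might also not be pre-program. Section 5.3 puts the optional self-directed activity at 1.5 months, before a Class 1 held at two months, while the schedule table puts it at Month 3. The two must be reconciled.

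Finally, averaging does not remove drift or a retest effect. If the second pre-score shifts by an amount d on average, the averaged baseline shifts by d/2. What the second score adds is the ability to see that shift. The burden objection stands too: the protocol gives no length for CAS or IRI, so the extra survey cannot be assumed short.

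**Conclusion.** A worthwhile low-cost improvement, not a defect. With dz = 0.4, two-sided alpha 0.05 and 60 complete pairs, power moves from about 86% to somewhere between 86% and 94%, depending on a noise share that the documents do not give. With 40 pairs, which low enrolment makes a relevant case, it moves from 69% to about 72-81% for a noise share of a quarter to all. These figures assume equal SDs, equal correlation of both pre-scores with the post-score, and no mean shift between the pre-scores.

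It would be wrong to conclude that the planned t-test is invalid or that the single baseline in itself biases it. The documents show a lost opportunity for precision and for a pre-exposure check, and no more than that.

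**What to change.** **Schedule (5.2, 5.3, 6.1 and the section 5 table).** For nurses who have not yet attended a class and whose class date leaves a gap after enrolment, resend CAS and IRI by REDCap in the 7 days before that class and before any program content. Reconcile the two timings of the optional activity so that this order can be guaranteed.

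**Analysis (9.3).** Test the post-program score minus the mean of the available pre-program scores, using the enrolment score alone where the second is missing. Report the enrolment-to-pre-class change as a check on drift and retest effects.

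**Sample size (9.2).** Correct the error probabilities, state the sidedness, and present any power gain as a range over the noise share and the return rate.

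**Cost.** One more survey and one more exposure to the items per nurse, a protocol/IRB modification and a short addition to 9.3. No visit, staff or participants are added. Track post-program completion, since losing more than about 3 to 14 of 60 pairs, depending on the noise share, would cancel the gain.

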5.3 Intermediate Visits

Art Immersion Class 1 (1-2 months from baseline)

- In-person workshop at the MET

Optional Self-Directed Activity (1.5 months from baseline)

- Independent self-directed reflective exercise with art materials and prompts provided by the MET.

Art Immersion Class 2 (3-4 months from baseline)

- Virtual workshop with MET staff via WebEx

Art Immersion Class 3

- Additional in-person workshop at the MET, added due to low enrollment in previous sessions

Art immersion Class 4

- Additional virtual workshop with MET staff via WebEx, for same reason as above

5.4 Final Study Visit

Final Data Collection (6 months from baseline)

- 6-month CAS and IRI surveys
- Post-program qualitative evaluation survey

5.5 Withdrawal Visit

No visit is required for withdrawal, participant may cease participation at any time

5.6 Unscheduled Visit

N/A

CONFIDENTIAL

This material is the property of the NYU Langone Health. Do not disclose or use except as authorized in writing by the study sponsor

Observational Study Template Version: 18 July 2022

6 Study Procedures/Evaluations

6.1 Procedures/Evaluations

After consent has been obtained, the following will take place:

- Participants will be asked to provide their email or cell phone of choice so we may communicate study information, reminders, and surveys via email or text message.
- Participants will then be asked to complete a demographic survey, the Interpersonal Reactivity Index (IRI) and the Cultural Assessment Survey (CAS).
 - The demographic survey contains questions about age, race/ethnicity, gender, years of nursing experience, NYULH campus, specialty, shift time, and role (clinical or nurse leader).
 - CAS measures cultural awareness, sensitivity, knowledge and skills.
 - IRI measures four separate aspects of empathy and its relationships with measures of social functioning, self-esteem, emotionality, and sensitivity to others.
- Following completion of the surveys, participants will be asked to sign up for 2 art immersion classes. Participants will be offered 4 dates to sign up for the art immersion classes. An additional set of one in-person class and one virtual class will be added due to low enrollment. The first class will be an in-person class at the Metropolitan Museum of Art (MET) located on [name]. The second class will be virtual via WebEx. Each class will last 60 minutes.
- There will also be an optional independent self-directed reflective exercise with art materials and prompts provided by the MET.
- At 7 months (after second class), participants will be asked to complete the IRI and the CAS surveys again. Participants will also be asked to complete a short qualitative survey about the overall impact of the art immersion program on your work and life.

Museum educators from The MET will be providing the curriculum that will include an art immersion program that will select specific works/art in the museum as well as virtually that will help to stimulate self-reflection and prompt connection to their nursing practice. MET staff will be conducting workshops as part of their paid job and will not be engaged in human subjects research as researchers.

7 Adverse Events

7.1 Definitions

Unanticipated Problems Involving Risk to Subjects or Others

Any incident, experience, or outcome that meets all of the following criteria:

- Unexpected in nature, severity, or frequency (i.e. not described in study-related documents such as the IRB-approved protocol or consent form, the investigators brochure, etc)
- Related or possibly related to participation in the research (i.e. possibly related means there is a reasonable possibility that the incident experience, or outcome may have been caused by the procedures involved in the research)

CONFIDENTIAL

This material is the property of the NYU Langone Health. Do not disclose or use except as authorized in writing by the study sponsor

Observational Study Template Version: 18 July 2022

- Suggests that the research places subjects or others at greater risk of harm (including physical, psychological, economic, or social harm).

Adverse Event

An **adverse event** (AE) is any symptom, sign, illness or experience that develops or worsens in severity during the course of the study.

Serious Adverse Event

Adverse events are classified as serious or non-serious. A **serious adverse event** is any AE that is:

- fatal
- life-threatening
- requires or prolongs hospital stay
- results in persistent or significant disability or incapacity

All adverse events that do not meet any of the criteria for serious should be regarded as **non-serious adverse events**.

Post-study Adverse Event

All unresolved adverse events should be followed by the investigator until the events are resolved, the subject is lost to follow-up, or the adverse event is otherwise explained.

7.2 Recording of Adverse Events

At each contact with the subject, the investigator must seek information on adverse events by specific questioning and, as appropriate, by examination. Information on all adverse events should be recorded immediately in the source document, and also in the appropriate adverse event module of the case report form (CRF). All clearly related signs, symptoms, and abnormal diagnostic procedures results should be recorded in the source document, though should be grouped under one diagnosis.

All adverse events occurring during the study period must be recorded. The clinical course of each event should be followed until resolution, stabilization, or until it has been determined that the study treatment or participation is not the cause. Serious adverse events that are still ongoing at the end of the study period must be followed up to determine the final outcome. Any serious adverse event that occurs after the study period and is considered to be possibly related to study participation should be recorded and reported immediately.

7.3 Reporting of Serious Adverse Events and Unanticipated Problems

For Narrative Reports of Safety Events

If the report is supplied as a narrative, the minimum necessary information to be provided at the time of the initial report includes:

• Study identifier• Study Center• Subject number• A description of the event• Date of onset	
• Current status• Whether study treatment was discontinued• The reason why the event is classified as serious• Investigator assessment of the association between the event and study treatment
---	--

7.3.1 Investigator reporting: notifying the IRB

Federal regulations require timely reporting by investigators to their local IRB of unanticipated problems posing risks to subjects or others. The following describes the NYULMC IRB reporting requirements, though Investigators at participating sites are responsible for meeting the specific requirements of their IRB of record.

CONFIDENTIAL

This material is the property of the NYU Langone Health. Do not disclose or use except as authorized in writing by the study sponsor

Report Promptly, but no later than 5 working days:

Researchers are required to submit reports of the following problems promptly but no later than 5 working days from the time the investigator becomes aware of the event:

- ***Unanticipated problems including adverse events that are unexpected and related***
 - *Unexpected: An event is “unexpected” when its specificity and severity are not accurately reflected in the protocol-related documents, such as the IRB-approved research protocol, any applicable investigator brochure, and the current IRB-approved informed consent document and other relevant sources of information, such as product labeling and package inserts.*
 - *Related to the research procedures: An event is related to the research procedures if in the opinion of the principal investigator or sponsor, the event was more likely than not to be caused by the research procedures.*
 - *Harmful: either caused harm to subjects or others, or placed them at increased risk*

Other Reportable events:

The following events also require prompt reporting to the IRB, though ***no later than 5 working days:***

- ***Complaint of a research subject*** when the complaint indicates unexpected risks or the complaint cannot be resolved by the research team.
- ***Protocol deviations or violations*** (includes intentional and accidental/unintentional deviations from the IRB approved protocol) for any of the following situations:
 - *one or more participants were placed at increased risk of harm*
 - *the event has the potential to occur again*
 - *the deviation was necessary to protect a subject from immediate harm*
- ***Breach of confidentiality***
- ***Incarceration of a participant*** when the research was not previously approved under Subpart C and the investigator believes it is in the best interest of the subject to remain on the study.
- ***New Information indicating a change to the risks or potential benefits*** of the research, in terms of severity or frequency. (e.g. analysis indicates lower-than-expected response rate or a more severe or frequent side effect; Other research finds arm of study has no therapeutic value; FDA labeling change or withdrawal from market)

Reporting Process

The reportable events noted above will be reported to the IRB using a Reportable New Information submission and will include a description of the event with information regarding its fulfillment of the above criteria, follow-up/resolution, and need for revision to consent form and/or other study documentation. Copies of each report and documentation of IRB notification and receipt will be kept in the Clinical Investigator's study file.

8 Study Oversight

It is the responsibility of the Principal Investigator to oversee the safety of the study at her site. This monitoring will include careful assessment and appropriate reporting of adverse events as noted above, as well as the construction and implementation of a data monitoring plan. The PI has experience in leading art immersion programs in collaboration with The MET and will have the support needed by [name], RN, who is the System Senior Director of Nursing Research to ensure that the integrity of the research protocol is maintained across the campuses.

CONFIDENTIAL

This material is the property of the NYU Langone Health. Do not disclose or use except as authorized in writing by the study sponsor

9 Statistical Considerations

